### **6.3 INTERCURRENT EVENTS**

The expected intercurrent events (ICEs) of interest in this trial are:

- Use of the following restricted concomitant therapy:
  - NO-sGC-cGMP pathway activating therapies like NO-donors (e.g. glyceryl trinitrate, isosorbide di- or mono-nitrate, molsidomine), PDE-5-inhibitors (e.g. sildenafil, tadalafil, and vardenafil), non-specific PDE inhibitors such as dipyridamole and theophylline, or sGC-stimulators (e.g., riociguat)
- New onset of / dose change in existing NSBB / carvedilol, pioglitazone, GLP1-agonists and vitamin E concomitant therapy
- Occurrence of a decompensation event
- Premature discontinuation of assigned trial medication

[figure not shown]
The strategies for handling those intercurrent events in this trial are as follows:

Treatment Policy: This is the effect of randomizing patients to a treatment arm regardless of treatment actually being taken. All intercurrent events will be handled according to the treatment policy approach as defined in ICH E9(R1). This will be used as the **primary strategy** of implementing the Estimand Concept (EC).

### **6.4 SUBJECT SETS ANALYSED**

The subject sets will be used as defined in the CTP, Section 7.2.1. These include the Treated set (TS) and Full analysis set (FAS).

- Screened set (SCR) – this analysis set includes all patients having signed informed consent. The SCR will be used for analyses of patient disposition.

The discussion on all exceptional cases and problems and the decisions on the allocation of patients to populations will be made at latest at DBLM.

In [Table 6.4:1](#) the subject sets which are to be used for each class of endpoint are illustrated.

Table 6.4: 1 Subject sets analysed

	Subject set		
Class of endpoint	SCR	TS	FAS
Disposition	X		
Primary endpoint			X
Secondary efficacy endpoints			X
Safety endpoints & treatment exposure		X	
Demographic/baseline endpoints		X	

## **Handling of Treatment Misallocations in Analysis Sets**

If a subject entered the trial but was not treated, they will be reported under their randomised/assigned treatment group for efficacy analysis according to FAS. Such subjects are excluded from the safety analyses since no study medication was taken.

If a subject is randomised but took incorrect treatment during the study,

- For efficacy analyses according to the FAS, subjects who took incorrect treatment will be reported under their randomised treatment group.
- For safety analyses based on TS, the actual treatment will be used as below:
  - o If a patient took at least one dose of empagliflozin, then the patient will be reported under the treatment group of avenciguat + empagliflozin.

## 6.6 HANDLING OF MISSING DATA AND OUTLIERS

### 6.6.1 Efficacy data

No imputation of missing data is planned for the efficacy endpoints.

## 6.6.2 Safety data

Missing safety data will not be imputed.

### **6.6.3 Missing dates and times**

Missing or incomplete AE dates are imputed according to company standards [\(2\)](#).

If the date of first drug administration is missing but the patient was entered, the date of the first drug administration will be set to the date of entering the trial. If the date of first administration is partially missing with the month and year present, the day will be set to the date of entering the trial if entering the trial was in the same month. If entering the trial was in the month prior to the first drug administration the missing day will be imputed as the first day of the month.

Partial start and stop dates for concomitant therapies will be imputed to enable subsequent calculation (but not for display) by the following “worst case” approach:

[figure not shown]
- If the day of the end date is missing, then the end date is set to last day of the month (or to the patient’s trial completion date, whichever is earlier).
- If the day and month of the end date are missing, then the end date is set to 31st of December of the year (or to the patient’s trial completion date if it is earlier than 31st December of the year).
- If the day of the start date is missing, then the start date is set to first day of the month.
- If the day and month of the start date are missing, then the start date is set to 1st January of the year.

All other cases need to be assessed by the trial team on an individual basis, using above points as guidance.

### **6.6.4 Time since first diagnosis**

For incomplete information on the date of the first diagnosis (both of cirrhosis and of chronic liver disease), time since first diagnosis will be calculated as follows:

- If the year of first diagnosis is unknown, then the time since diagnosis will be set to missing.
- If day and month of the first diagnosis are unknown, time since first diagnosis will be calculated as if diagnosed on the 30th June of that year.
- If only the day of the first diagnosis is unknown, time since diagnosis will be calculated as if diagnosed on the 15th of that month.

## **6.7 BASELINE, TIME WINDOWS AND CALCULATED VISITS**

Regarding efficacy and safety endpoints, the term “baseline” refers to the last observed measurement prior to administration of any study medication.

Measurements taken prior to the first intake of study medication will be considered pre-treatment values. Pre-treatment values will be assigned to a visit according to the nominal visit number as recorded on the eCRF or as provided by the laboratory.

In general, the date of the first drug administration will be used to separate pre-treatment from on-treatment values. Measurements taken after first trial medication intake will be considered on-treatment values if they have been obtained up to end of the parameter specific follow-up period as defined in [Table 6.7:1](#) below and will be assigned to the corresponding study medication for efficacy and safety analyses.

Measurements taken after the end of the endpoint specific follow-up period will be considered post-treatment values.

Table 6.7: 1 Parameter specific follow-up period for the assignment to treatment phase

Endpoint	Last day of assignment to treatment phase (days after study medication stop date)
Efficacy	
HVPG	8 (REP + 1)
A large black rectangular box used to redact sensitive information.	
Safety	
Adverse events	7
Safety laboratory measurements	3
Vital signs (including body weight, blood pressure)	1

For derivation of the last value on treatment, minimum value on treatment, and maximum value on treatment, all values from the relevant phase (whether or not collected in any time window; see [Table 6.1:1](#) for definition of the trial phases) will be considered; these will be derived for analysis of laboratory and vital signs data. For identification of potentially clinically significant abnormal laboratory values, all values (whether selected in any time window) up to 7 days after last treatment intake will be considered.

On-treatment efficacy, safety [REDACTED] measurements will be assigned to visits based on the extended time windows around the planned visit dates, defined relative to the day of first trial medication intake (see [Table 6.7:2](#)).

Table 6.7: 2 Time windows for assignment of measurements to visits for statistical analysis

Visit number /name	Visit label	Planned day B	Time window (Days)				
			Window (per CTP)	Start (per CTP)	End (per CTP)	Start (extended)*	End A (extended) #
V1	Screening	-42				-∞	0
On-treatment							
V2	Week 0	Day 1	N/A	1	1	≤1	1
V3	Week 1	Day 8	+2	8	10	2	11
V4	Week 2	Day 15	[contact]
V5	Week 4	Day 29	[contact]
V6	Week 6	Day 43	±3	40	46	37	50
V7	Week 8/ EoT	Day 57	±3	54	60	51	Study medication stop date + X C days
Off-treatment							
V8	Week 12/ EoS	Day 85	±5	80	90	Study medication stop date + X days+1	Day of last follow-up

A In case of premature discontinuation of the study medication, an early EoT visit has to be performed within 7 days of medication stop date. If such an EoT Visit falls into the time window of a previous visit, measurements will be assigned to this previous visit and the visit value will be determined as described above. In this case, the time window for the visit that includes the early EoT visit will end X days after the study medication stop date, including Day X. Patients will then be asked to continue in the study according to the visit schedule. Off-treatment measurements will be assigned to visits in the same manner.

B Days are counted relative to the day of first treatment, which is defined as Day 1.

\* Start (extended): End of extended window of last visit+1

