If Visit 1b and 1c are performed on the same day, the HVPG measurement must be performed after the gastroscopy (i.e. only once it is confirmed that the patient remains eligible for the trial). At the EoT visit, the HVPG measurement should be performed on the day of the scheduled visit, or within seven days (if this latter approach is taken, the measurement should still be performed after an overnight fast / after a fast of at least four hours). If this scenario is chosen for an HVPG performed during the treatment period, the morning dose of trial medication can be taken prior to the procedure. In the event of early discontinuation from the trial, refer to [Section 6.2.2.1](#) for guidance regarding the HVPG measurement at the ED visit.

*A summary of the HVPG procedure is as follows ([R20-3977](#)):*

Under local anaesthesia and ultrasound guidance, a catheter introducer sheath is placed in the right internal jugular vein. Using fluoroscopic guidance, a balloon catheter is advanced into

Proprietary confidential information © 2023 Boehringer Ingelheim International GmbH or one or more of its affiliated companies

the inferior vena cava (IVC) and inserted into a large hepatic vein. Correct and sufficient wedge position of the catheter is ensured by injecting contrast media while the balloon is blocking the outflow of the cannulated hepatic vein. After calibrating the external pressure transducer, continuous pressure recordings are obtained with triplicate recordings of the WHVP and FHVP. The difference between FHVP and WHVP is referred to as HVPG, with values  $\geq 10$  mmHg indicating CSPH. Before removing the catheter, pressure readings obtained in the IVC at the same level, as well as the right atrial pressure, are recorded.

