#### **6.2.2 Treatment period(s)**

If a patient is deemed eligible for the trial following Visits 1a, 1b and 1c, the patient will be randomised at Visit 2 (Day 1) by using the IRT system. All Visit 2 assessments (refer to the [Flow Chart](#)) should have been completed prior to administration of the first dose of trial medication; exceptions are the post-dose vital signs and ECGs [REDACTED]  
Each patient can be randomised only once into the trial. The randomised treatment period starts with Visit 2 and ends when a patient reaches the EoT visit (refer to the [Flow Chart](#)). The last dose of BI 685509 will be administered in the evening of the day before the EoT visit and the last dose of empagliflozin in the morning of the day before the EoT visit.

Patients will be assessed regularly at scheduled visits as specified in the [Flow Chart](#). During the dose titration phase of the treatment period (refer to [Section 4.1.4](#)), scheduled visits are more frequent. It is of particular importance that the time window for these visits is adhered to since the patient must have taken the preceding dose of BI 685509 for at least seven consecutive days before any up-titration occurs (refer to Sections [4.1.4](#), [4.1.4.1](#) and [4.1.4.2](#)). Unscheduled visits may also be arranged where necessary; assessments completed during an unscheduled visit will depend on the circumstances under which the visit was planned, and should be based on Investigator judgement.

[REDACTED] Patients should also be reminded to bring [REDACTED] the electronic BP and HR monitoring device with them to each trial visit (refer to [Sections 5.2.2.1](#) and [5.6.1](#)). Refresher training should be provided as required.

At every dispensing visit in the trial (refer to [Flow Chart](#)), an IRT call should be made.

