# End (extended): Midpoint of planned days between current visit and next visit

C X is the parameter specific follow-up period for the assignment to treatment phase, refer to [Table 6.7:1](#) for the details.

The midpoint between two on-treatment visits defines the end of a time window, with the midpoint being included in the time window of the preceding visit. The end of the time window of the last on-treatment visit (end of treatment (EoT)) is endpoint dependent ([Table 6.7:1](#)).

Repeated and unscheduled efficacy and safety measurements will be assigned to the nominal visits and listed in the subject data listing according to the time windows described above. Only one observation per time window will be selected for analysis at an on-treatment visit - the value which is closest to the protocol planned visit day will be selected. If there are two

observations which have the same difference in days to the planned day, the first value will be selected. If there are two observations on the same day, the first value will be selected. If there are multiple values within the time window of the last visit, including a value on the last day of drug intake, the value on the last day of drug intake is used as the value of the last visit.

Data prior to Day 1 of trial medication will be based on nominal visits and time windowing will not be applied. For these time points, data from the scheduled visit will always be selected if they are collected correctly. Unscheduled visits will only be considered if no correct data from the scheduled visit is available. If no correct data from a scheduled visit is available and multiple unscheduled correct values are available for a visit, the first correct value will be selected.

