#### **7.4.1 Main analysis**

For the primary endpoint, the analysis of covariance (ANCOVA) will be used. The analysis will be performed on the FAS and include on-treatment HVPG only. If a patient misses the Week 8 visit, the missing data will not be imputed.

[figure not shown]
The statistical model will be:

Percentage HVPG change from baseline at Week 8 = overall mean + HVPG baseline + treatment + random error

This model includes treatment as fixed classification effects and baseline HVPG as a linear covariate. The random error is assumed to be normally distributed with mean 0 and variance  $\sigma^2$ . The analysis will only be used for estimation of treatment effects without performing statistical tests.

The main analysis will implement the primary estimand defined in [Section 6.3](#) and be performed on FAS. All data collected after the intercurrent events will be used for the analysis. The number of patients reporting each type of intercurrent event will be summarized for overall and each treatment group.

If after all the steps above have been investigated without successful model convergence, then an ANCOVA (Analysis of Covariance) model at Week 8 only, will be performed. If the above sequence of methods does not lead to convergence for a particular subgroup, then that analysis will not be performed or reported.

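### An EoT HVPG done before the visit and on or before Day 50 would be filed as Week 6 and lost to the primary analysis; protocol 5.1.1 and SAP 6.1/6.7 do not agree on whether this can happen

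*SAP*

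**What the plan says.** - **Visit assignment (SAP 6.7).** On-treatment values, efficacy included, are sorted by day since first dose: "measurements will be assigned to visits based on the extended time windows around the planned visit dates". In Table 6.7:2 the Week 6 row reads "Week 6 Day 43 ±3 40 46 37 50", so its extended window is Days 37 to 50. The EoT row begins "Week 8/ EoT Day 57 ±3 54 60 51", so its extended window opens on Day 51. The table notes set each boundary at the midpoint of the planned days, "with the midpoint being included in the time window of the preceding visit".
- **HVPG-specific limit (SAP Table 6.7:1).** Only the closing end is tailored to HVPG, at 8 days after the medication stop date. No separate opening day is given.
- **HVPG timing (protocol 5.1.1).** At EoT, "the HVPG measurement should be performed on the day of the scheduled visit, or within seven days". The protocol then adds: "If this scenario is chosen for an HVPG performed during the treatment period, the morning dose of trial medication can be taken" before the procedure.
- **Treatment period (protocol 6.2.2).** "The randomised treatment period starts with Visit 2 and ends when a patient reaches the EoT visit", and the last BI 685509 dose is given on the evening before that visit. The Flow Chart has one post-baseline HVPG, at EoT, which is planned for Day 57 ± 5.
- **The SAP's reading (SAP 6.1).** Citing protocol 5.1.1, it restates the seven days as counted after the scheduled EoT. SAP 4 declares no changes from the protocol's methods.
- **Primary analysis (SAP 7.4.1).** The ANCOVA is for Week 8 only and uses on-treatment HVPG: "If a patient misses the Week 8 visit, the missing data will not be imputed".

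**The concern.** The primary endpoint rests on one invasive measurement after baseline. If that measurement is taken ahead of the EoT visit and falls on or before Day 50, the day windows label it Week 6. The rule that picks the value closest to the planned day works only within a window, so it cannot bring the value back. The patient then has no Week 8 HVPG, drops out of the ANCOVA, and cannot be classed as a responder on the Week 8 value. The patient still counts in the responder denominator, because SAP 7 bases percentages on everyone in the set.

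The two documents differ on whether this can arise. Protocol 5.1.1 contains a sentence that has a use only for an HVPG before EoT, while SAP 6.1 assumes that the allowance runs only afterwards. The trial is open-label, so the filing of an early value is better settled in writing than case by case once values are known.

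**Working it through.** **1. Reproduce the window boundary.** The planned days are 43 (Week 6) and 57 (Week 8). The midpoint is (43 + 57)/2 = 50, which belongs to the earlier visit, so Week 8 opens on Day 51. This matches Table 6.7:2.

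**2. Which direction do the seven days run?** The documents give these pieces:
- The only post-baseline HVPG is at EoT (Flow Chart).
- The treatment period ends at EoT, and the last BI 685509 dose is the evening before (protocol 6.2.2).
- Protocol 5.1.1 nevertheless provides for an HVPG within treatment, on a day when a morning dose has been taken.

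A completing patient takes no morning dose on or after the EoT day, so that sentence has a use only if the HVPG precedes EoT. This is an inference. The protocol does not say so outright.

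**3. Days affected under each reading.** EoT may fall on Days 57 − 5 = 52 to 57 + 5 = 62.
- *After EoT only (SAP 6.1):* HVPG falls on Days 52 to 62 + 7 = 69. None is before Day 51, so nothing is misfiled.
- *Either side of EoT:* HVPG falls on Days 52 − 7 = 45 to 69. The misfiled days run from EoT − 7 to 50, which is 50 − (EoT − 7) + 1 = 58 − EoT days.

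| EoT day | HVPG days filed as Week 6 (either-side reading) | Count |
|---|---|---|
| 52 | 45–50 | 6 |
| 53 | 46–50 | 5 |
| 54 | 47–50 | 4 |
| 55 | 48–50 | 3 |
| 56 | 49–50 | 2 |
| 57 | 50 | 1 |
| 58–62 | none | 0 |

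With the ± 3 window printed in the SAP table (EoT on Days 54 to 60), the affected days would be 47 to 50.

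**4. The late end.** The stop date is EoT − 1, so EoT + 7 equals the stop date + 8. This is exactly the SAP limit, and no permitted late HVPG is cut off.

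**5. Illustrative cost.** Protocol 7.5 gives an SD of 25% and at least 20 patients in each of groups 3 and 4. The losses below are assumed.
- One value is 1/20 = 5% of a 20-patient group. If that patient would have been a responder, the reported rate falls by 5 percentage points.
- The 95% half-width of a simple group mean with 20 patients is 2.093 × 25/√20 = 11.7 points. With 18 it is 2.110 × 25/√18 = 12.4 points.
- The protocol's probability of observing a mean reduction of at least 10% when the truth is 20% is Φ(10/(25/√20)) = 96.3%, which reproduces its figure. With 18 patients it is 95.5%.

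**The case against.** A reader might infer that the protocol plainly permits an HVPG in the week before EoT, and that compliant values on Days 45 to 50 will therefore be lost. The documents do not support that, for four reasons.

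- Protocol 5.1.1 gives no direction. The pre-EoT reading comes from one sentence about the morning dose combined with the last-dose rule. The SAP authors, citing the same section, read it as after EoT, and on that reading the effect disappears.
- Days 45 to 49 need two allowances stacked: an EoT visit earlier than Day 57, and an HVPG well before it. If the scheduled visit in protocol 5.1.1 means planned Day 57, only Day 50 is exposed.
- The trial is descriptive with no hypothesis test, no bias has been shown, and two assumed losses in a group of 20 change precision only slightly.
- The midpoint rule is a consistent convention stated in advance. How early a value may be and still represent Week 8 is a matter of judgement: Day 45 is 2 days after planned Week 6 and 12 days before planned Week 8.

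All four points stand, and they limit the size and certainty of the concern. They do not remove it. The morning-dose sentence has no evident use under the after-only reading, and the amendment log adds it in the same entry that settles on two HVPG measurements. No SAP text exempts HVPG from the day windows.

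**Conclusion.** The point holds conditionally. If an EoT HVPG is done before the visit and falls on or before Day 50, the SAP as written removes the patient's only post-baseline value from the primary ANCOVA and from the Week 8 responder derivation. This rests on the inferred pre-EoT reading of protocol 5.1.1. Under the after-only reading of SAP 6.1, no value is lost. Exposure is one day at the planned EoT, at most six days at the earliest permitted EoT, and none from Day 58 onwards. The documents give no basis for estimating how many patients this would concern, and it may be none.

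This is therefore a low-cost safeguard for the primary endpoint, and it does not show that the analysis is invalid. The ± 3 days that Table 6.7:2 attributes to the protocol for EoT, against ± 5 in the Flow Chart, is a separate labelling error. It does not move the Day 51 opening, which comes from the planned days.

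**What to change.** 1. In SAP 6.7, add that the single post-baseline HVPG performed for the EoT visit is assigned to Week 8 by its nominal visit, subject to the existing on-treatment limit (stop date + 8 days), and that its actual study day is listed. Confine this to EoT. Protocol 6.2.2.1 does not require an HVPG at an early discontinuation visit, and any such value should not become Week 8 through this rule.
2. State one direction for the seven days, in the same terms, in protocol 5.1.1 and SAP 6.1.
3. In Table 6.7:2, correct the per-protocol EoT window from ± 3 (Days 54–60) to ± 5 (Days 52–62).

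Opening the HVPG Week 8 window at Day 45 is not recommended. It builds the extreme case into the table and would claim any HVPG from that day on, whatever visit it was done for. Nominal assignment works under either reading of the seven days.

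The cost is a sentence or two and one table row in the SAP, plus a wording clarification in the protocol. The downside is small: a few values from slightly before Week 8 may count as Week 8, and the listed study day makes them visible.

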# End (extended): Midpoint of planned days between current visit and next visit

C X is the parameter specific follow-up period for the assignment to treatment phase, refer to [Table 6.7:1](#) for the details.

The midpoint between two on-treatment visits defines the end of a time window, with the midpoint being included in the time window of the preceding visit. The end of the time window of the last on-treatment visit (end of treatment (EoT)) is endpoint dependent ([Table 6.7:1](#)).

Repeated and unscheduled efficacy and safety measurements will be assigned to the nominal visits and listed in the subject data listing according to the time windows described above. Only one observation per time window will be selected for analysis at an on-treatment visit - the value which is closest to the protocol planned visit day will be selected. If there are two

observations which have the same difference in days to the planned day, the first value will be selected. If there are two observations on the same day, the first value will be selected. If there are multiple values within the time window of the last visit, including a value on the last day of drug intake, the value on the last day of drug intake is used as the value of the last visit.

Data prior to Day 1 of trial medication will be based on nominal visits and time windowing will not be applied. For these time points, data from the scheduled visit will always be selected if they are collected correctly. Unscheduled visits will only be considered if no correct data from the scheduled visit is available. If no correct data from a scheduled visit is available and multiple unscheduled correct values are available for a visit, the first correct value will be selected.

